2.6.1 Replacement of Missing Data

The last observation carried forward (LOCF) principle will be utilized for the analysis of NYHA Classification and Patient Global Assessment for primary endpoint 1 and secondary endpoints 2 and 3.

Missing NYHA and patient global assessment data at either the enrollment or follow-up visits affects the number of subjects that can be included in the analysis. It is possible that subjects or study personnel may either forget or choose not to answer one or more of the questions related to NYHA classification or patient global assessment.

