2.2 Subject Status Definitions

The subject status definitions utilized in this study are provided in Table 3.

Table 3: Subject Status Definitions

Subject Status	Definition
Provisionally enrolled	
Subject has provided written informed consent but has not yet been screened against the MPP sub-study specific inclusion and exclusion criteria.
 
Provisionally enrolled subjects will become fully enrolled if they meet the MPP sub-study specific inclusion and exclusion criteria, and complete the MPP Enrollment visit.
 
Provisionally enrolled subjects will not be included in the analysis population for the study objectives; however, they may be included in analysis of additional data of interest.

Screen Failure	
Subject has signed consent, but at the time of consent it was identified the subject does not meet all inclusion/exclusion criteria,
 
OR
 
Subject consented prior to implant, but prior to implant the subject status changes.
 
Subject will be exited and will not be included in the analysis population or count toward the enrollment maximum.

Fully Enrolled	
Subject meets all of the MPP sub-study specific inclusion criteria and none of the exclusion criteria, and completes the MPP Enrollment visit.
 
Fully enrolled subjects will be included in the analysis population for the study objectives, as well as in the analysis of the additional data of interest.

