2.3 Study Size and Duration

The MPP sub-study will enroll up to 110 subjects at up to 75 sites within the United States who are participating in the QP ExCELS study. Based on the previous sample size analysis for the post-approval QP ExCELS cohort, the sample size for the QP ExCELS study is 1754 and will remain unchanged to support continuation of the MPP sub-study (QP ExCELS protocol version February 1, 2017 provides the justification and sample size analysis).

Subjects that enroll in the MPP sub-study will be followed 12 months post-implant, while subjects that do not continue in the MPP sub-study will be followed for 6 months post-implant.

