2.5 Adjustments to Overall Sample Size

Due to the inclusion of interim analyses, a total of 90 evaluable subjects are required to demonstrate superiority to a performance goal of 3%. Assuming a 10% loss to follow-up rate during the study for reasons unrelated to the study outcomes, a total enrollment of 100 subjects would be required to achieve an evaluable study population of 90 subjects.

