2.6 Data Analyses

Descriptive statistics will be used to present and summarize the data collected in the clinical study. Frequency distributions and cross tabulations will be presented for discrete variables. Means, standard errors, and ranges will be presented for continuous variables.

Classification of "HF hospitalization" and "cardiovascular death" events for use in primary endpoint 1, secondary endpoint 2, and secondary endpoint 3 analyses will be determined by a Clinical Events Committee (Section 5.1.1.).

For primary endpoint 1, the lower, one-sided, exact 97.5% bound for the observed proportion of responders ("improved") would have to exceed 3% for rejection of the null hypothesis. Additionally, descriptive statistics will be provided for observed

changes in NYHA class and frequency tabulations provided for the other components of the Clinical Composite Score.

The AE-free rate calculated for secondary endpoint 1 will be based on the total number of subjects with at least one MPP related adverse event requiring additional invasive intervention to resolve. For the secondary endpoint analysis, the AE classification, category, resolution, and relation to the MPP feature for each individual event will be determined by the Clinical Events Committee (CEC) (Section 5.1.1). All adverse events which the CEC determines the event is related or possibly related to the MPP feature will be included in the secondary endpoint 1 analysis. Adverse events with a final CEC adjudicated relation of not related or unknown will not contribute to or be included in the evaluation of the secondary endpoint.

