2.6.2 MPP Sub-Study Analysis Population

The primary and secondary endpoint analyses will be conducted according to the intention-to-treat principle (ITT) utilizing all available data from fully enrolled subjects. Subjects are expected to remain programmed with the MPP feature ON from MPP enrollment through the completion of the sub-study. Subjects who have the MPP feature permanently turned OFF prior to completion of the sub-study will be required to report a protocol violation; however, these subjects will be included in the analysis population. All available data from subjects that undergo a pulse generator change and no longer have an MPP eligible device will be included in the analysis. Subjects may have the MPP feature temporarily turned OFF due to a lead revision procedure and these short durations with MPP will not be reported as a protocol violation.

Any QP ExCELS subject that does not enroll into the MPP sub-study but receives MPP due to the physician's determination will not be analyzed towards the MPP study endpoints.

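### LOCF in 2.6.1 is not limited to post-enrollment values, so a never-followed subject can be a Secondary Endpoint 3 responder; and with all fully enrolled subjects analysed, the 80% power at 100 enrolled does not hold

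*Combined protocol and SAP*

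**What the plan says.** - **Missing data (2.6.1).** "The last observation carried forward (LOCF) principle will be utilized for the analysis of NYHA Classification and Patient Global Assessment for primary endpoint 1", and likewise for Secondary Endpoints 2 and 3. No source visit is named or excluded. The next paragraph adds that missing NYHA or PGA at enrollment or follow-up "affects the number of subjects that can be included in the analysis".
- **Population.** Table 3 in 2.2: "Fully enrolled subjects will be included in the analysis population for the study objectives". Section 2.6.2 analyses "according to the intention-to-treat principle (ITT) utilizing all available data from fully enrolled subjects".
- **Classification (2.1.1, 2.1.3, 2.1.4).** Response at the 6-month MPP visit is judged against the MPP enrollment visit. The primary counts only Improved. Secondary Endpoint 3 also counts Unchanged. Secondary Endpoint 2 adds the PGA.
- **PGA (3.2.6, 3.3.5).** It is first taken at MPP enrollment and asks about change since before CRT, not since MPP was switched on.
- **Sample size (2.3.1.1, 2.5).** 90 evaluable subjects for 10% against a 3% goal. With 10% lost "for reasons unrelated to the study outcomes", "a total enrollment of 100 subjects would be required to achieve an evaluable study population of 90 subjects". Section 2.3 sets the ceiling: "The MPP sub-study will enroll up to 110 subjects".
- **Success rule (2.6).** "the lower, one-sided, exact 97.5% bound for the observed proportion of responders" must exceed 3%.

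**The concern.** LOCF needs a rule on whether the baseline value may be carried. Here the baseline is also the comparator, so carrying it compares a value with itself and returns Unchanged. Endpoint 3 treats Unchanged as a response to MPP during follow-up, so a subject never seen again can be reported as a responder. In Endpoint 2, a subject who already felt better than before CRT when MPP was switched on can be reported as Improved with no assessment under MPP.

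The second issue is consistency between sizing and analysis. Section 2.5 treats lost subjects as leaving the analysis, while Table 3 and 2.6.2 keep them in. If they stay, the primary is tested on a larger denominator than the one for which 80% power was derived, and the exact test may then need one more improved subject.

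**Working it through.** **Inputs.** From 2.3.1.1: null rate 3%, expected rate 10%, one-sided 0.025, 80% power, 90 evaluable. From 2.4: final nominal level 0.0224. From 2.5: 10% loss, 100 enrolled. From 2.3: ceiling 110. Assumed, because the documents give no figures: the observed response rates for Endpoints 2 and 3, and the enrollment PGA distribution.

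**1. The plan's own figure.** The exact one-sided binomial test against 3% on n = 90 rejects with 7 or more improved: P(X ≥ 7 | 90, 3%) = 0.0188. Power is P(X ≥ 7 | 90, 10%) = 80.75%. 90 is the smallest n with exact power of at least 80%, and 90 / (1 − 0.10) = 100. The stated sizes reproduce; at 0.0224 the cut-off and power on 90 are the same.

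**2. Primary with all fully enrolled subjects analysed.** At 0.025 the cut-off is 7 improved up to n = 95 and 8 from n = 96 to 110. At 0.0224 the step falls between 93 and 94. Seven improved gives:

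| n | p | Exact 97.5% lower bound |
|---|---|---|
| 90 | 0.0188 | 3.18% |
| 95 | 0.0245 | 3.01% |
| 96 | 0.0257 | 2.98% |
| 100 | 0.0312 | 2.86% |

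So 100 analysed subjects need 8. If the rate is 10% among those followed and no lost subject is improved, power is P(X ≥ 8 | number followed, 10%):

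| Enrolled | Lost | Followed | Power |
|---|---|---|---|
| 100 | 10 | 90 | 68.9% |
| 100 | 5 | 95 | 74.5% |
| 100 | 0 | 100 | 79.4% |
| 110 | 11 | 99 | 78.5% |
| 110 | 0 | 110 | 87.0% |

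The fall from 80.75% to 68.9% is the probability of exactly 7 improved among 90, 11.9%. At 110 enrolled with up to 14 lost (110 − 14 = 96), both denominators need 8, so the choice does not alter the decision if no lost subject improves.

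**3. Primary under the carried enrollment value.** Enrollment NYHA carried to month 6 gives Unchanged, which is not a response in 2.1.1. This is conservative.

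**4. Secondary Endpoint 3.** Take 100 enrolled, 10 lost before any follow-up without a qualifying event, and response rate q among the other 90. Carrying enrollment NYHA gives (90q + 10)/100, a shift of 10(1 − q) points. Counting the 10 as non-responders gives 90q/100, a shift of −10q points.

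| q (assumed) | Enrollment value carried | Lost as non-responders |
|---|---|---|
| 50% | 55% (+5) | 45% (−5) |
| 70% | 73% (+3) | 63% (−7) |
| 90% | 91% (+1) | 81% (−9) |

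**5. Secondary Endpoint 2.** Let r be the observed rate and g the share of the 10 whose enrollment PGA was better or markedly better. The shift is (90r + 10g) − 100r = 10(g − r) points. At g = 50% it is +2, 0 and −2 for r of 30%, 50% and 70%, so the direction is not fixed.

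**The case against.** **The two parts exclude each other.** If the enrollment value is carried, every fully enrolled subject has a class, because NYHA is obtained at screening (3.3.4, 3.3.8.1), and the denominator is settled. If lost subjects are dropped, nothing is carried for them. This stands: they are consequences of alternative readings and must not be added together.

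**The plan already names its population.** A reader might infer that the primary denominator is wholly open and could be chosen after the data are seen. The documents do not support that. Table 3 and 2.6.2 are explicit. The observed proportion in 2.6 is the ordinary term for a sample proportion, and the second paragraph of 2.6.1 can be read as the reason for replacing values. What remains is that 2.5 does not match the stated population.

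**The effects are limited.** A reader might infer that LOCF inflates the primary result. For never-followed subjects it does the opposite. Endpoints 2 and 3 have no performance goal, so the effect is on a reported estimate, not a test. The 69% figure requires that none of the 10 lost subjects carries an improved month-3 value. All this stands and limits the weight of the point.

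**LOCF conventionally excludes baseline.** Possibly, but 2.6.1 does not say so, and its reference to missing data at either visit does not settle it.

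**Other deaths.** A reader might also see an error where a death not classed as cardiovascular leaves the carried class in place. The composite counts cardiovascular death by design, so this is a matter of preference.

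**Conclusion.** The point holds in this form, and the plan should be amended. As written, 2.6.1 applied to the stated population makes a never-followed, event-free subject an Endpoint 3 responder. The overstatement is 10(1 − q) points with 10 such losses in 100, and half that with 5. It assumes that all these losses precede any follow-up and that the observed rate represents the lost subjects. Endpoint 2 is exposed too, in an unknown direction.

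For the primary, 80% power at 100 enrolled with 10% loss holds only if lost subjects are dropped. Under the stated population it is about 69% to 79% at 100, and about 78% to 87% at 110, assuming a 10% rate among those followed and no improvement credited to those lost. The validity of the primary test is not in question.

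**What to change.** 1. **2.6.1:** carry forward only post-enrollment NYHA and PGA values; in practice, month 3 to month 6.
2. **2.6.1 and 2.5:** state that the primary denominator is all fully enrolled subjects, with those who have no post-enrollment NYHA counted as not improved. This gives the same primary result as carrying the enrollment NYHA, so it only writes the rule down. Restate power as about 69% to 79% at 100 enrolled and 78% to 87% at 110.
3. **Secondary Endpoints 2 and 3:** a subject with a CEC-adjudicated HF hospitalization or cardiovascular death is Worsened and stays in every rate, whether or not NYHA or PGA was obtained. Report two rates side by side:
   - among subjects with such an event or with the post-enrollment values the endpoint needs (NYHA for Endpoint 3; both NYHA and PGA for Endpoint 2);
   - over all fully enrolled subjects, with the remainder as non-responders.

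   Do not keep or omit a subject with only one Endpoint 2 measure according to what that measure shows.
4. **Optional:** a sensitivity analysis counting deaths not classed as cardiovascular as non-responses, with the endpoint definition unchanged.

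The cost is wording in 2.5 and 2.6.1, a few extra tabulations and a less favourable stated power. No new data and no change to the response classes are needed. Both secondary rates are shown because, if losses are unrelated to outcome as 2.5 assumes, the non-responder version is itself too low (5 to 9 points for Endpoint 3 in the illustration).

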2.6.2 MPP Sub-Study Analysis Population

The primary and secondary endpoint analyses will be conducted according to the intention-to-treat principle (ITT) utilizing all available data from fully enrolled subjects. Subjects are expected to remain programmed with the MPP feature ON from MPP enrollment through the completion of the sub-study. Subjects who have the MPP feature permanently turned OFF prior to completion of the sub-study will be required to report a protocol violation; however, these subjects will be included in the analysis population. All available data from subjects that undergo a pulse generator change and no longer have an MPP eligible device will be included in the analysis. Subjects may have the MPP feature temporarily turned OFF due to a lead revision procedure and these short durations with MPP will not be reported as a protocol violation.

Any QP ExCELS subject that does not enroll into the MPP sub-study but receives MPP due to the physician's determination will not be analyzed towards the MPP study endpoints.

3. PROTOCOL REQUIREMENTS

3.1 Subject Population

The subject population consists of heart failure subjects with CRT-D indication according to clinical routine.

Up to 1754 subjects will be enrolled in the clinical investigation. The investigator is responsible for screening all potential subjects and selecting those who are appropriate candidates for enrollment in the QP ExCELS clinical study. The subjects selected for participation should be from the investigator's general patient population with documented evidence of an indication for implantation of a BIOTRONIK CRT-D system according to clinical routine and according to the inclusion and exclusion criteria described below. Decision for implantation of the respective BIOTRONIK devices is based on medical decisions alone and should not be influenced by the possible enrollment to this clinical trial.

The implanting physician is responsible for choosing the fixation and length variant. For the indications, we recommend following the respective current guidelines of the Heart Rhythm Society (HRS), the American College of Cardiology (ACC), and the American Heart Association (AHA), as well as those of other national cardiology associations.

Investigators are strongly encouraged to seek equal enrollment between men and women at their site. This will help ensure women are adequately represented in the study population and enable meaningful analyses of results by gender.

3.1.1 Indications for Use

The Sentus OTW QP left ventricular pacing lead is a 4.8 French (5 F introducer) quadripolar steroid-eluting lead intended for permanent implantation in the left ventricle via the coronary veins to provide pacing and/or sensing when used in conjunction with a compatible IS4 pulse generator.

3.1.2 Contraindications

Implantation of this lead is contraindicated in the following cases:

- Coronary sinus anomalies
- Tissue in the coronary sinus area that has been damaged by an infarction
- Any anomalies of the venous system that preclude transvenous implantation of the lead
- Patient cannot tolerate a single systemic dose of up to 0.5 mg of dexamethasone acetate (DXA)

3.1.3 Inclusion Criteria

All of the following inclusion criteria have to be fulfilled for participation in the QP ExCELS Study:

- Standard CRT-D indication according to clinical routine
- *De novo* implantation or upgrade from existing ICD or pacemaker implant utilizing a BIOTRONIK Ilivia 7 HF-T QP family CRT-D system or Acticor/Rivacor HF-T QP family CRT-D system. feature with IS4 LV port and Sentus QP LV lead, that meets one of the following criteria:
 - Implant planned to occur after enrollment
 - Enrollment occurs within 30 days after implant and NYHA from within 30 days prior to implant is documented in subject medical record
- Patient is able to understand the nature of the clinical investigation and provide written informed consent
- Patient is able and willing to complete all routine study visits at the investigational site up to 12 months of follow-up
- Able to understand the nature of the study and give informed consent
- Available for follow-up visits at the investigational site, including those specific to the MPP sub-study
- Age \geq 18 years

At the time of MPP screening for inclusion into the MPP sub-study, additional inclusion criteria have to be fulfilled for participation:

- Successfully implanted with a BIOTRONIK Ilivia 7 HF-T QP family CRT-D system or Acticor/Rivacor HF-T QP family CRT-D system. Successful implantation is defined as having at least two LV pacing vectors with a measured pacing threshold of ≤ 5.0 V @ any pulse width (allowing for a minimum 2.5 V safety margin) without phrenic nerve stimulation at the final programmed pacing output at the time of enrollment into the MPP sub-study.
- CRT Responder Assessment classification as “Worsened” or “Unchanged”
- Standard continuous biventricular (BiV) pacing from implant until MPP enrollment

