1.2 Background

Heart failure (HF) is a major public health issue with a current prevalence of 2-3% in the total and 10-20% in the aged population (Lloyd-Jones et al., 2010). The overall prevalence for heart failure is increasing due to aging population. Additional factors are the success of the modern therapies in prolongation of survival of patients suffering from coronary events and the effective prevention of death for patients being at high risk.

The overall mortality for the population is 50% in the first 4 years and 40% of the patients with HF-related hospitalizations have to be readmitted to hospital or die within one year (Dickstein et al., 2008).

Cardiac Resynchronization Therapy (CRT) is used in order to synchronize interventricular and intraventricular contraction pattern of the heart in patients with heart failure in whom there is evidence of electrical dyssynchrony (QRS width ≥ 120 ms). CRT with defibrillator function (CRT-D) is recommended to reduce morbidity and mortality in patients in NYHA class III-IV who are symptomatic despite optimal medical therapy and suffer from a reduced left ventricular ejection fraction (LVEF $\leq 35\%$, (Dickstein et al., 2008)). This indication has been recently extended to patients in NYHA class II (Dickstein et al., 2010).

Despite the proven benefit of CRT in the indicated population, up to one-third of patients do not respond to the therapy (Rinaldi et al., 2015). The combination of the BIOTRONIK left ventricular lead family Sentus QP with the corresponding Cardiac Resynchronization Therapy devices (CRT) provides additional pacing options to optimize cardiac resynchronization therapy, based on the individual anatomy and needs of heart failure patients as well as the ability of stimulating more than one LV pacing site within one cardiac cycle.

Studies have shown that multiple point LV pacing via a QP LV lead may be an alternative approach to improve CRT response by delivering multiple LV pacing pulses, simultaneously recruiting a larger volume of myocardium (Forleo et al., 2016). A recent IDE study from St. Jude Medical showed that quadripolar multiple point LV pacing (MultiPoint™ Pacing algorithm) was non-inferior to standard quadripolar biventricular (BiV) pacing (Tomassoni et al., 2016).

The current protocol is designed to demonstrate the effectiveness of the MPP feature in BIOTRONIK CRT-D systems by converting a percentage of CRT non-responders to responders.

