2.1 Objectives

The primary objective of this clinical investigation is to demonstrate that the MPP feature is effective by converting a percentage of CRT non-responders to responders. Each subject's responder status will be assessed using a Clinical Composite Score (CCS) including three components: NYHA Class, heart failure (HF) hospitalizations, and cardiovascular death (Packer et al., 2001).

The MPP sub-study also includes three secondary endpoints.

2.1.1 Primary Endpoint 1

The purpose of primary endpoint 1 is to evaluate the CRT responder status with the MPP feature within the Ilivia 7 HF-T QP family CRT-D or Acticor/Rivacor 7 HF-T QP family CRT-D system, compared to a pre-specified performance goal.

The associated hypothesis is evaluated based on a CCS determining a responder classification based on changes in NYHA class, HF hospitalization, and cardiovascular death.

A responder status will be derived classifying these subjects as "Improved", "Worsened", or "Unchanged" using the following definitions.

Responder Classification at the 6-Month MPP Follow-up (evaluated compared to MPP enrollment visit):

- "Improved":
 - No HF hospitalization or cardiovascular death, AND
 - NYHA class is improved
- "Unchanged":
 - No HF hospitalization or cardiovascular death, AND
 - NYHA class is unchanged
- "Worsened":
 - HF hospitalization or cardiovascular death has occurred, OR
 - NYHA class is worsened

Ho: The proportion of subjects (P) who are classified as "Improved" is not superior to a performance goal (PG) of 3%.

$$PG \geq P$$

Ha: The proportion of subjects who are classified as "Improved" is superior to a performance goal of 3%.

$$PG < P$$

A rejection of the null hypothesis would indicate that the proportion of subjects classified as “Improved” is superior to 3%.

2.1.2 Secondary Endpoint 1

The purpose of Secondary Endpoint 1 is to evaluate adverse events that require additional invasive intervention to resolve, specifically related to the MPP feature of the Ilivia or Acticor/Rivacor HF-T QP family. These adverse events include any software issues related to MPP programming or any adverse event that occurs while MPP is enabled and that may be attributed to the use of the MPP feature.

2.1.3 Secondary Endpoint 2

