The purpose of Secondary Endpoint 2 is to evaluate a modified CCS, determining a responder classification based on changes in NYHA class, Patient Global Assessment (PGA), HF hospitalization, and cardiovascular death, where the PGA will ask subjects to assess how their overall status has changed since prior to receiving CRT therapy (markedly better, better, unchanged, worse, markedly worse).

Modified Responder Classification (CCS + PGA) at the 6-Month MPP Follow-Up (evaluated compared to MPP enrollment visit):

- “Improved”:
 - No HF hospitalization or cardiovascular death, AND
 - Neither NYHA class is worsened or PGA is worsened (“worse” or “markedly worse”), AND
 - NYHA class is improved or PGA is improved (“better” or “markedly better”)
- “Unchanged”:
 - No HF hospitalization or cardiovascular death, AND
 - NYHA class is unchanged, AND
 - PGA is unchanged (“unchanged”)
- “Worsened”:
 - HF hospitalization or cardiovascular death has occurred, OR
 - NYHA class is worsened or PGA is worsened (“worse” or “markedly worse”)

2.1.4 Secondary Endpoint 3

The purpose of Secondary Endpoint 3 is to evaluate the Responder Classification (as defined in Section 2.1.1) in which both “Improved” and “Unchanged” subjects will be classified as responders. At the time of enrollment into the MPP sub-study, MPP sub-study subjects have already been found to have no change or worsening in their HF status with BiV pacing. Since HF is a chronic and progressive condition,

these subjects may be expected to continue to worsen during the MPP follow-up period or remain stable with careful management. In this secondary endpoint, a status of “Unchanged” (in addition to “Improved”) during the MPP follow-up period will be considered a responder to MPP.

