3.2.5 New York Heart Association (NYHA) Classification

During the course of the study, the NYHA classification will be utilized for evaluation of the specific level of cardiac disease. The NYHA will be evaluated at all protocol-defined follow-ups. The following bullets provide the definitions for each class:

- Class I: Subjects with cardiac disease, but without resulting limitation of physical activity. Ordinary physical activity does not cause undue fatigue, palpitation, dyspnea, or anginal pain.

- Class II: Subjects with cardiac disease resulting in slight limitation of physical activity. They are comfortable at rest. Ordinary physical activity results in fatigue, palpitation, dyspnea, or anginal pain.
- Class III: Subjects with cardiac disease resulting in marked limitation of physical activity. They are comfortable at rest. Less than ordinary activity causes fatigue, palpitation, dyspnea, or anginal pain.
- Class IV: Subjects with cardiac disease resulting in inability to carry on any physical activity without discomfort. Symptoms of cardiac insufficiency or of anginal syndrome may be present even at rest. If any physical activity is undertaken, discomfort is increased.

The description for each of the classes was taken from the ACC/AHA Guidelines for Implantation of Cardiac Pacemakers and Antiarrhythmia Devices (Gregoratos et al., 1998).

[figure not shown]

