3.3.5 MPP Sub-Study Enrollment

MPP sub-study enrollment occurs after a subject has been screened and determined to meet all MPP sub-study specific inclusion criteria and none of the exclusion criteria. QP ExCELS subjects with a heart failure hospitalization will be considered to have a CRT Responder Assessment classification of worsened and are eligible for the MPP sub-study. Subjects with a heart failure hospitalization occurring prior to the 6 month post-implant follow-up visit may be enrolled between 3 and 6 months post-implant by completing an interim follow-up eCRF (Section 3.3.8.1) or be enrolled at the QP ExCELS 6 month follow-up visit (Section 3.3.4).

MPP optimization may be performed or not performed per investigator discretion at the time of enrollment into the MPP sub-study. The investigator will determine if MPP optimization will be performed for each subject and which method will be used (e.g. QRS width, electrical delay, echocardiography, etc.). MPP programmed parameters may be adjusted as needed during the follow-up period for MPP sub-study subjects.

After a patient has been screened and determined to be eligible for the MPP sub-study, the following data will be collected:

1. Turn MPP ON and collect MPP programmed settings
2. Document MPP optimization method
3. Obtain Patient Global Assessment
4. Document any reportable Adverse Events
5. Review and complete the appropriate eCRFs

The MPP feature must be programmed ON from MPP enrollment until the subject exits the sub-study. Subjects who have the MPP feature permanently turned OFF prior to completion of the sub-study will be required to report a protocol violation.

3.3.6 3-Month MPP Follow-up

At a 3-month MPP follow-up (90 ± 30 days post-MPP enrollment), subjects return to the investigational site for an in-office assessment of their heart failure status and implanted system.

The following data should be collected:

1. Collect MPP programmed settings
2. Obtain NYHA classification and HF hospitalization status
3. Obtain Patient Global Assessment
4. Collect device initial and final programmed settings
5. Document any reportable Adverse Events
6. Review and complete the appropriate eCRFs

3.3.7 6-Month MPP Follow-up

At the 6-month follow-up (180 ± 30 days post-MPP enrollment), subjects return to the investigational site for an in-office assessment of their heart failure status and implanted system.

1. Collect MPP programmed settings

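### The MPP sub-study sets no minimum NYHA class, so a subject in class I at MPP enrollment can enter, can never be classed as improved, and stays in the primary denominator

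*Combined protocol and SAP*

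**What the plan says.** **Entry.** The parent study requires a "Standard CRT-D indication according to clinical routine" (Section 3.1.3) and names no NYHA class. The sub-study adds a "CRT Responder Assessment classification as" worsened or unchanged, judged against the QP ExCELS enrollment visit (Section 2). Under Section 3.3.5, "subjects with a heart failure hospitalization will be considered to have a CRT Responder Assessment classification of worsened and are eligible", whatever the NYHA class at that visit. Neither Section 3.1.3 nor Section 3.1.4 sets a NYHA floor.

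**Primary endpoint.** Section 2.1.1 counts a subject as a success only if there is no heart failure hospitalization or cardiovascular death and "NYHA class is improved". The classification is "evaluated compared to MPP enrollment visit". The NYHA scale in Section 3.2.5 starts at "Class I: Subjects with cardiac disease, but without resulting limitation of physical activity".

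**Analysis set.** All fully enrolled subjects are analyzed by intention to treat (Table 3 in Section 2.2; Section 2.6.2).

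**Secondary Endpoint 3.** Under Section 2.1.4 a subject who is unchanged "will be considered a responder to MPP".

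**Sample size.** Section 2.3.1.1 sets a 3% goal, an expected 10%, one-sided 0.025, 80% power and 90 evaluable subjects. It mentions neither a NYHA ceiling nor a class I share.

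**The concern.** The sub-study asks whether MPP converts non-responders. Entry is judged against the QP ExCELS enrollment visit, but success is judged against the MPP enrollment visit. A subject whose class at the second visit is I meets the definition of a non-responder and has no better class to move to. That subject is a certain primary failure, whatever MPP does.

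Two things are at stake:

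- **Power.** The plan needs 7 improved subjects in 90 and has less than one point of power to spare above 80%. Subjects who cannot succeed use part of the enrollment cap of 110.
- **Interpretation.** The same subject, if stable and event-free, is a failure in the primary and a responder in Secondary Endpoint 3. Neither result says anything about conversion.

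**Working it through.** **1. Can a class I subject enter?** There are two routes.

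- Class I at QP ExCELS enrollment and class I at the MPP enrollment visit, with no hospitalization: unchanged, so eligible.
- A heart failure hospitalization since implant: worsened, so eligible in any class. A subject who went from class III to class I but was hospitalized qualifies this way.

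NYHA worsening is not a route, because a subject cannot worsen into class I.

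**2. Reproducing the plan's 90.** Inputs from Sections 2.3.1.1 and 2.4: null rate 3%, expected rate 10%, final one-sided level 0.0224, interim level 0.0026 at 45 subjects.

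- Final rule: the smallest x with P(X ≥ x | n=90, p=0.03) ≤ 0.0224. P(X ≥ 6) = 0.0539 and P(X ≥ 7) = 0.0188, so 7 improved subjects are needed. The count is also 7 at level 0.025.
- Interim rule: P(X ≥ 5 | n=45, p=0.03) = 0.0110 and P(X ≥ 6) = 0.0022, so 6 are needed.
- Single-stage power at 10%: 80.75%. At 89 subjects it is 79.8%, and 90 is the smallest n that reaches 80%.
- Two-stage power at 10% (stop at ≥6/45, otherwise ≥7/90): 80.9%. Two-stage type I error: 0.0192.

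The stated 90 is reproduced.

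**3. Effect of a class I share f.** The documents give no value for f, so the values below are assumptions. The 10% can be read in two ways.

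*Reading A: 10% is the rate among subjects able to improve (class II-IV).* The overall rate is P = 0.10 × (1 − f).

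*Reading B: 10% is the rate over all enrolled non-responders.* Power stays at 80.9%, and the class II-IV rate must be 0.10 / (1 − f).

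| f (assumed) | A: overall rate | A: two-stage power, n=90 | B: class II-IV rate needed |
|---|---|---|---|
| 0% | 10.0% | 80.9% | 10.0% |
| 2% | 9.8% | 79.2% | 10.2% |
| 5% | 9.5% | 76.4% | 10.5% |
| 10% | 9.0% | 71.2% | 11.1% |
| 15% | 8.5% | 65.4% | 11.8% |

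Under reading A, two-stage power drops below 80% at a share of just over 1%. At f = 10%, the smallest number of evaluable subjects with 80% single-stage exact power is 113, which exceeds the enrollment cap of 110.

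**4. Secondary Endpoint 3.** Let q1 and q be the proportions who do not worsen in class I and in class II-IV. The overall rate is (1 − f)q + f·q1, so the shift caused by class I subjects is f(q1 − q). With assumed f = 10%, q1 = 90% and q = 70%, it is 0.10 × 0.20 = +2 points. It is zero if q1 = q and negative if q1 < q.

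**The case against.** **The share is probably small.** Section 1.2 describes the CRT-D indication as class III-IV and adds "This indication has been recently extended to patients in NYHA class II". Class I is not mentioned, so class I at both visits should be rare, and the hospitalization route accounts for most of what remains. At 2% the loss is 80.9 − 79.2 = 1.7 points, less than the discreteness of the exact test: moving from 90 to 99 evaluable subjects raises the critical count from 7 to 8 and lowers single-stage power from 80.8% to 78.5%. This stands, and it limits the size of the point.

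**The 10% may already cover these subjects.** Section 2.3.1.1 ties the estimate to all-comer non-responders, which favors reading B. This also stands: a loss of power against the stated 80% is conditional, not shown. The section's reasons for a low expectation, however, are that the cited pivotal study of a competing system included responders and selected subjects by echocardiography. Nothing shows that a NYHA ceiling was considered.

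**All-comer entry was deliberate, and changing eligibility during enrollment makes the population less uniform.** True, but the stated reason for all-comer entry is that echocardiographic screening is not routine. That reason does not bear on admitting subjects who cannot meet the endpoint.

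**A stronger reading of Secondary Endpoint 3.** A reader might infer that class I subjects inflate this endpoint by their full contribution to the numerator. The documents do not support that. The same subjects are also in the denominator, the net shift is f(q1 − q), and its sign is unknown: those who entered after a hospitalization may be at higher risk of worsening. Counting stability as response is an explicit choice that applies in every class, and the endpoint has no hypothesis or performance goal.

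**Conclusion.** The point holds in a limited form. The criteria admit subjects in class I at MPP enrollment, the endpoint definition makes them certain primary failures, and the analysis set keeps them in the denominator. All three follow from the text without any assumption.

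The cost in power depends on two things the documents leave open: the class I share and the population that the 10% describes. Under reading A the loss is 1.7 points at a 2% share, 4.5 points (80.9 − 76.4) at 5% and 9.7 points (80.9 − 71.2) at 10%. Under reading B nothing is lost, but the class II-IV rate has to be higher than 10%, and the plan does not say so.

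A reader might also infer that the primary test is invalid. It is not: these subjects can only count against the feature, so type I error is not raised. In Secondary Endpoint 3 the matter is one of labeling, with a net effect of unknown direction and no test affected. This is an inexpensive improvement, not a flaw that undermines the trial.

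**What to change.** 1. For remaining enrollment, add to the sub-study criteria in Section 3.1.3 a NYHA class at MPP enrollment that leaves room to improve, that is, class II or higher.
2. Keep the ITT primary analysis in all fully enrolled subjects, including any class I subjects already enrolled.
3. Pre-specify in Section 2.6 the primary and Secondary Endpoint 3 results in subjects in class II-IV at MPP enrollment as supportive, and report the class I count.
4. State in Section 2.3.1.1 whether the 10% describes all enrolled non-responders or only those able to improve. If class I subjects remain eligible, state the expected share and size the study on the resulting overall rate.

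The cost is one eligibility line, one sentence on the assumption and one extra table. NYHA class is already obtained at the visits where subjects are screened (Sections 3.3.4 and 3.3.8.1), so no new data are needed. The downside is that a few subjects become ineligible and the population is slightly less all-comer.
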